Temozolomide	Zofran 4-8 mg or other anti-emetic as needed	150- 200mg/m2	РО	Daily for 5 consecutive days in cycles 3-4

5.2 **Pre-Treatment Criteria**

5.2.1 Cycle 1, Day 1

Prior to administration of the first dose of bavituximab on day 1 of cycle 1, participants must meet the following criteria:

- Signed informed consent
- Demographic information, medical history and concurrent medication list
- Physical examination including mini-mental status examination, vital signs, height, weight, and Karnofsky performance status
- Laboratory work meeting the eligibility criteria must be obtained.

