5.2.2 Subsequent Days (Chemoradiation)

Prior to administration of the subsequent doses of bavituximab during chemoradiation participants must meet the following criteria. Patients can continue bavituximab if temozolomide is held for temozolomide related toxicity:

- Platelet count \geq 75,000/mcL
- WBC \geq 2,500/mcL
- No other bavituximab treatment related toxicities CTCAE grade > 2 (except for not maximally treated nausea and vomiting)
- If a bavituximab cannot be administered because of toxicity, there is a +3 day window to treat, otherwise the dose will be skipped and the patient resume dosing the next week if criteria met.
- 5.2.3 Subsequent Cycles of temozolomide (Post-chemoradiation cycles) Prior to administration of the subsequent doses of temozolomide participants must meet the following criteria within the windows outlined in the Study Calendar in Section 10:
 - Resolution of all grade 3 non-hematologic AEs (except for not maximally treated nausea and vomiting) to grade ≤ 1
 - Absolute neutrophil count (ANC) < grade 2
 - Platelet count \geq 100,000/mcL
 - Hemoglobin $\geq 8.0 \text{ g/dL}$
 - White blood cell (WBC) count $\geq 2,500/mcL$

- AST/SGOT and ALT/SGPT ≤ 2.5 x upper limit of normal (ULN)
- Serum total bilirubin ≤ 1.5 x ULN (unless patient has Gilbert's syndrome in which total bilirubin should be ≤ 2 xULN)
- Serum creatinine $\leq 1.5 \text{ x ULN}$ or 24-hour creatinine clearance $\geq 60 \text{ ml/min}$
- No other temozolomide related toxicities CTCAE grade >2
- If AEs persist, the start of the cycle may be delayed up to 30 consecutive days. If all AEs have not resolved to grade ≤ 1 after a 30-day delay, any further study treatment will be discontinued.
- For C3 and C4 when monthly temozolomide starts, bavituximab should be administered within 5 days of Day 1 of the temozolomide
- 5.2.4 Subsequent Cycles of bavituximab (Post-chemoradiation cycles)

Prior to administration of the subsequent doses of bavituximab participants must meet the following criteria within the windows outlined in the Study Calendar in Section 10. Patients can continue bavituximab if temozolomide is held for temozolomide related toxicity:

- Resolution of all grade 3 non-hematologic AEs (except for not maximally treated nausea and vomiting) to grade ≤ 2 thought related to bavituximab
- Platelet count \geq 75,000/mcL
- Hemoglobin $\ge 8.0 \text{ g/dL}$
- White blood cell (WBC) count $\geq 2,500/mcL$
- AST/SGOT and ALT/SGPT ≤ 2.5 x upper limit of normal (ULN)

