5.3.2 Other Agent(s)

Temozolomide will be taken per standard of care. Guidelines provided below on dosing/schedule.

Temozolomide During Concomitant Radiation Therapy

Temozolomide will be administered continuously from day 1 of radiotherapy to the last day of radiotherapy at a daily oral dose of 75 mg/m² for a maximum of 42 days. The drug will be administered orally 1-3 hours before each session of radiotherapy during weekdays (Monday through Friday). During weekends without radiotherapy (Saturday and Sunday), the drug will be taken in the morning. The dose will be determined using actual body surface area (BSA) as calculated in square meters at the beginning of the concomitant treatment.

Patients will be instructed to swallow the capsules whole, in rapid succession, without chewing them. If vomiting occurs during the course of treatment, no re-dosing of the patient is allowed before the next scheduled dose. The capsules should be taken on an empty stomach, therefore a minimum of 2 hours after eating and with no food consumption for at least 1 hour after temozolomide administration. Although, nightly administration just before bedtime has been reported to improve tolerance, the low daily dose administered during radiation is very well tolerated and administration in the morning before radiation dosing is required for this protocol. Administration of the higher dosing regimen during the adjuvant phase of the protocol should be performed using the nightly administration.

Antiemetic prophylaxis is usually not required for the continuous daily dosing schedule (during radiation). However, prophylaxis with a 5-HT3 antagonist is recommended 30-60 minutes prior to administration of the first few temozolomide doses. Most patients report optimal nausea control with the use of a 5-HT3 antagonist. Routine use of antiemetics is recommended during the adjuvant phase of treatment. Additionally, pneumocystis carinii prophylaxis is at the discretion of the Investigator during the radiation phase.

Post-Radiation Temozolomide Dosing

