As part of this protocol, patients will receive up to 2 cycles of adjuvant temozolomide at a dose of 150-200 mg/m2 days 1-5 of a 28-day cycle. Patients will be treated for up to 6 months of post-RT temozolomide (Stupp 2005). If patients experience grade 3 or higher toxicity attributable to the temozolomide that does not resolve to a grade 2 or less within 60 days of the last temozolomide dose, temozolomide should be discontinued. If the toxicity returns to a grade 2 or less within 30 days of the last dose, temozolomide can be dose reduced to 150mg/m2. The active period of this clinical trial will be approximately 18 weeks as long as there are no delays or missed doses that need to be made up.

As part of this protocol, temozolomide will be administered orally once per day for 5 consecutive days (days 1-5) of a 28-day cycle. The starting dose for the first cycle will be 150 mg/m²/day, with a single dose escalation to 200 mg/m²/day in subsequent cycles if no treatment-related adverse events > Grade 2 are noted. Patients can be increased to 200 mg/m2 at any time during the maintenance phase if deemed clinically appropriate by the treating physician.

The start of the cycle 2 will be scheduled 28 days \pm 7 days after the last day of radiotherapy. The start of the subsequent cycles (Cycles 3-4) will be scheduled in 28 days \pm 7 days) after the first daily dose of temozolomide of the preceding cycle.

The dose will be determined using the BSA per institutional standard.

Patients will be instructed to fast at least 2 hours before and 1 hour after temozolomide administration. Water is allowed during the fast period. Patients will be instructed to swallow the capsules whole, in rapid succession, without chewing them. Treatment can be given at night if patient prefers.

If vomiting occurs during the course of treatment, no re-dosing of the patient is allowed before the next scheduled dose.

If a patient misses the dose of temozolomide, it made be made up within 8 hours, otherwise the dose should be delayed until the next time it is due. Missed doses can be added on to the end of the 5 day dosing (i.e. taken on day 6) during the maintenance phase (i.e. 5/28 day cycles).

Antiemetic prophylaxis with a 5-HT3 antagonist is recommended and should be administered 30 to 60 minutes before temozolomide administration. Temozolomide should be stored at room temperature.

5.3.3 Other Modality(ies) or Procedures

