6. DOSING DELAYS/DOSE MODIFICATIONS

Dose delays and modifications will be made as indicated in the following table(s). The descriptions and grading scales found in the revised NCI Common Terminology Criteria for Adverse Events (CTCAE) version 4.0 will be utilized for dose delays and dose modifications. A copy of the CTCAE version 4.0 can be downloaded from the CTEP website http://ctep.cancer.gov/protocolDevelopment/electronic_applications/ctc.htm.

If temozolomide is held, bavituximab can continue if the adverse event is deemed to be unlikely related to bavituximab. There will be no change in dosing schedule or assessment schedule if either drug is held.

Nausea	Management/Next Dose for temozolomide
≤ Grade 1	No change in dose
Grade 2	Hold until \leq Grade 1. Resume at same dose level.
Grade 3	Hold [*] until < Grade 2. Resume at one dose level lower, if indicated. ^{**}

Nausea	Management/Next Dose for temozolomide		
Grade 4	Off protocol therapy		
*Participants requiring a delay of >30 days should go off protocol therapy.			
**Participants requiring > two dose reductions should go off protocol therapy.			
Recommended manag	ement: antiemetics.		

Vomiting	Management/Next Dose for temozolomide
≤ Grade 1	No change in dose
Grade 2	Hold until \leq Grade 1. Resume at
	same dose level.
Grade 3	$Hold^*$ until < Grade 2. Resume at
	one dose level lower, if indicated.**
Grade 4	Off protocol therapy
*Participants requiring	a delay of >30 days should go off pr
**Participants requirin	g > two dose reductions should go of
Recommended manag	gement: anti-emetics.

Neutropenia	Management/Next Dose for temozolomide	
\leq Grade 1	No change in dose	
Grade 2	Hold until \leq Grade 1. Resume at	
Ofade 2	same dose level.	
Grade 3	$Hold^*$ until < Grade 2. Resume at	
Glade 5	one dose level lower, if indicated.**	
Grade 4	Off protocol therapy	
	g a delay of >30 days should go off pro	
*Participants requirin	g > two dose reductions should go off	f protocol therapy

Thrombocytopenia	Management/Next Dose for temozolomide		
\leq Grade 1	No change in dose		
Grade 2	Hold until \leq Grade 1. Resume at same dose level.		
Grade 3	Hold [*] until < Grade 2. Resume at one dose level lower, if indicated. ^{**}		
Grade 4	Off protocol therapy		
*Participants requiring a delay of >30 days should go off protocol therapy. **Participants requiring > two dose reductions should go off protocol therapy.			

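### Section 5.3.2 gives 150 mg/m2 as the reduced temozolomide dose after severe toxicity, which is no reduction for a patient at the 150 mg/m2 starting dose, and read alone it allows a restart after grade 4 events that Section 6 takes off protocol therapy

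*Combined protocol and SAP*

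**What the plan says.** Section 5.3.2 introduces its temozolomide text with "Guidelines provided below on dosing/schedule". Under post-radiation dosing, the toxicity rule opens "If patients experience grade 3 or higher toxicity attributable to the temozolomide". If such toxicity falls to grade 2 or less within 30 days of the last dose, "temozolomide can be dose reduced to 150mg/m2". The next paragraph reads "The starting dose for the first cycle will be 150 mg/m²/day", with a single step up to 200 in later cycles if no treatment-related event above grade 2 has occurred. The treating physician may also raise the dose to 200 at any time in maintenance. The Section 5.1 regimen table gives 150 to 200 mg/m2, "Daily for 5 consecutive days in cycles 3-4".

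Section 6 states that its tables determine delays and modifications. For grade 3 nausea, vomiting, neutropenia or thrombocytopenia, temozolomide is held and then "Resume at one dose level lower, if indicated". Grade 4 in any of the four tables means off protocol therapy. A footnote removes patients who need more than two reductions. The dose-level table for cycles 3 and 4 lists 100 (level -1, for prior toxicity), 150 (level 0) and 200 (level +1).

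Section 5.2.3 sets the conditions for starting each adjuvant cycle. They include "Resolution of all grade 3 non-hematologic AEs (except for not maximally treated nausea and vomiting) to grade ≤ 1".

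**The concern.** A rule for restarting a cytotoxic drug after severe toxicity should lead to a dose below the one that caused the event, or say that the same dose is acceptable. Section 5.3.2 does neither for a patient at 150: its reduced dose is the dose the patient was already taking. The sentence is not limited to patients at 200.

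Level 100 appears only in the Section 6 table. Staff who dose from Section 5 see a range of 150 to 200 and would not learn that a lower level exists. Section 6 also asks that a temozolomide decrease be tried before bavituximab is stopped, and for a patient at 150 that decrease needs the 100 level.

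The trigger is the second problem. It includes grade 4, so the restart sentence reaches events for which Section 6 ends protocol therapy.

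At stake is the dose given to individual patients after a severe event, not the trial's inference.

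**Working it through.** No statistical formula applies. The check sets the two rules side by side for each dose a patient may be taking, then converts doses to course totals.

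**Inputs**
- Restart dose in Section 5.3.2: 150 mg/m2.
- Dose levels in Section 6: 100, 150 and 200 mg/m2/day.
- Days per adjuvant course: 5 (Sections 5.1 and 5.3.2).
- Protocol-dosed adjuvant cycles: up to 2, study cycles 3 and 4.
- Assumption: the Cycle 1 and Cycle 2 remarks in the Section 6 dose-level table mean the first and second adjuvant cycles, that is, study cycles 3 and 4. The table's own title supports this.

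**Which dose the patient is on.** Adjuvant dosing starts at 150, and scheduled escalation requires no treatment-related event above grade 2. A patient with a grade 3 event in study cycle 3 was therefore at 150, and that event blocks the scheduled step to 200. The exception is early discretionary escalation by the physician.

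**Side by side**

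| Situation | Section 5.3.2 | Section 6 (its four listed toxicities) |
|---|---|---|
| Grade 3, patient at 200 | 150 | 150, if indicated |
| Grade 3, patient at 150 | 150 (no reduction) | 100, if indicated |
| Grade 4 | restart at 150 permitted | off protocol therapy |

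**Course totals for a patient at 150**
- Section 5.3.2: 150 × 5 = 750 mg/m2.
- Section 6: 100 × 5 = 500 if the reduction is used, 750 if it is not.
- Difference: 750 − 750 = 0 up to 750 − 500 = 250 mg/m2. Maximum 250 / 750 = 33.3%.
- Over two cycles: 750 + 750 = 1500 against 750 + 500 = 1250 up to 1500. Maximum 250 / 1500 = 16.7%.

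**Course totals for a patient at 200.** The course before the event is 200 × 5 = 1000. The reduced dose that both sections name gives 150 × 5 = 750, so the difference between the sections is 0.

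**Reduction steps.** Section 6 offers two steps from 200 (to 150, then 100) and one from 150. Its allowance of two reductions makes sense only if 100 is a usable level. Section 5.3.2 names one step from 200 and none from 150.

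**The case against.** The strongest reply is that this is a gap which Section 6 fills, not a contradiction. A dose can be reduced to 150 only from above 150, so the sentence's own verb points to patients at 200, where the sections agree. For a patient at 150 the sentence gives no instruction, and the dedicated modification section supplies one in mandatory terms, whereas Section 5.3.2 describes itself as guidance. Both dose rules are permissive, nothing in Section 5.3.2 forbids 100, and the stricter Section 5.2.3 criteria gate each restart. The toxicity rule also follows a statement that post-radiation temozolomide runs for up to six months, and a patient who escalates would spend most of that time at 200.

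Much of this stands. Section 6 most likely governs, and a clinician who follows it reaches 100 when that is indicated. The six-month argument is weaker. The protocol doses only study cycles 3 and 4, and the Study Calendar leaves temozolomide from cycle 5 to institutional standard. On the scheduled path, the main in-protocol restart decision is the cycle 4 dose after a cycle 3 event, and that is a patient at 150. No precedence rule is stated, and the gap argument does not explain why a restart sentence should reach back to grade 4.

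A reader might infer that the two sections prescribe different lower doses for the same patient. They do not: at 150 Section 5.3.2 names no lower dose, and at 200 both name 150. A reader might also set a grade 4 course of zero under Section 6 against 750 under Section 5.3.2. That comparison requires ignoring Section 6. Moreover, leaving protocol therapy ends protocol dosing but leaves later care open under Section 5.5, so zero exposure cannot be derived.

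**Conclusion.** Wrong as written, and minor. The reduced dose in Section 5.3.2 is correct for a patient at 200 and is no reduction for a patient at 150. Its trigger also conflicts with Section 6 for grade 4 events in the four tabulated toxicities.

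For a patient at 150 the next course could differ by 0 to 33%, or 0 to 16.7% over the two protocol-dosed cycles. The upper figures assume that the reduction is judged indicated under Section 6 and that staff rely on Section 5.3.2 instead. The documents do not allow the number of affected patients to be estimated.

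It would go too far to say that Section 6 requires 100 after every temozolomide-related grade 3 event. Its tables cover four toxicities, the step is conditional, and adjuvant reductions are otherwise referred to the prescribing information. Nothing here touches OS12, alpha, power or sample size.

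**What to change.** Replace the restart sentence in Section 5.3.2 with: *Temozolomide may be resumed at the next lower level of the Section 6 dose-level table, if indicated (200 to 150, or 150 to 100 mg/m2), once the Section 5.2.3 recovery criteria are met; grade 4 events are handled under Section 6.*

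This keeps the conditional wording of Section 6 and creates no new obligation to reduce. Sections 5.2.3 and 6 each carry their own 30-day limit on delay, so a time limit remains. The neighbouring 60-day discontinuation rule in Section 5.3.2 is not addressed here and should be checked against those limits in the same edit.

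The cost is a one-sentence text amendment, with no new data, visits or patients.

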5.4 General Concomitant Medication and Supportive Care Guidelines

The case report form must capture the concurrent use of all other drugs, over-the-counter medications, or alternative therapies. There are no known drugs that have an interaction with bavituximab. Full dose anticoagulation is permitted although LMWH is preferred.

5.5 Criteria for Taking a Participant Off Protocol Therapy

Duration of therapy will depend on individual response, evidence of disease progression and tolerance. In the absence of treatment delays due to adverse event(s), treatment may continue for 18 weeks or until one of the following criteria applies:

- Disease progression
- Intercurrent illness that prevents further administration of treatment
- Unacceptable adverse event(s)
- Participant demonstrates an inability or unwillingness to comply with the oral medication regimen and/or documentation requirements
- Participant decides to withdraw from the protocol therapy
- General or specific changes in the participant's condition render the participant unacceptable for further treatment in the judgment of the treating investigator
- Completion of the 18 weeks of treatment and all study related MRI scans. However, patients may continue beyond 18 weeks at the discretion of the treating physician if the patient is deriving clinical benefit.

Participants will be removed from the protocol therapy when any of these criteria apply. The reason for removal from protocol therapy, and the date the participant was removed, must be documented in the case report form (CRF) and in OnCore. Alternative care options will be discussed with the participant.

In the event of unusual or life-threatening complications, treating investigators must immediately notify the Overall PI, [name] at [contact].

5.6 Duration of Follow Up

Participants will be followed every 3 months for 5 years from date of registration or until death, whichever occurs first. Participants removed from protocol therapy for unacceptable adverse event(s) will be followed until resolution or stabilization of the adverse event. Patients who do not continue to follow up in clinic will be reached by phone call to determine status. During this follow-up period, specific attention will be paid to any late effects of radiation which will be specifically captured on the case report forms.

5.7 Criteria for Taking a Participant Off Study

Participants will be removed from study when any of the following criteria apply:

- Lost to follow-up
- Withdrawal of consent for data submission
- Death

The reason for taking a participant off study, and the date the participant was removed, must be documented in the case report form (CRF). The research team should also update the relevant Off Treatment/Off Study information in OnCore.

6. DOSING DELAYS/DOSE MODIFICATIONS

Dose delays and modifications will be made as indicated in the following table(s). The descriptions and grading scales found in the revised NCI Common Terminology Criteria for Adverse Events (CTCAE) version 4.0 will be utilized for dose delays and dose modifications. A copy of the CTCAE version 4.0 can be downloaded from the CTEP website http://ctep.cancer.gov/protocolDevelopment/electronic_applications/ctc.htm.

If temozolomide is held, bavituximab can continue if the adverse event is deemed to be unlikely related to bavituximab. There will be no change in dosing schedule or assessment schedule if either drug is held.

Nausea	Management/Next Dose for temozolomide
≤ Grade 1	No change in dose
Grade 2	Hold until \leq Grade 1. Resume at same dose level.
Grade 3	Hold [*] until < Grade 2. Resume at one dose level lower, if indicated. ^{**}

Nausea	Management/Next Dose for temozolomide		
Grade 4	Off protocol therapy		
*Participants requiring a delay of >30 days should go off protocol therapy.			
**Participants requiring > two dose reductions should go off protocol therapy.			
Recommended manag	ement: antiemetics.		

Vomiting	Management/Next Dose for temozolomide
≤ Grade 1	No change in dose
Grade 2	Hold until \leq Grade 1. Resume at
	same dose level.
Grade 3	$Hold^*$ until < Grade 2. Resume at
	one dose level lower, if indicated.**
Grade 4	Off protocol therapy
*Participants requiring	a delay of >30 days should go off pr
**Participants requirin	g > two dose reductions should go of
Recommended manag	gement: anti-emetics.

Neutropenia	Management/Next Dose for temozolomide	
\leq Grade 1	No change in dose	
Grade 2	Hold until \leq Grade 1. Resume at	
Ofade 2	same dose level.	
Grade 3	$Hold^*$ until < Grade 2. Resume at	
Glade 5	one dose level lower, if indicated.**	
Grade 4	Off protocol therapy	
	g a delay of >30 days should go off pro	
*Participants requirin	g > two dose reductions should go off	f protocol therapy

Thrombocytopenia	Management/Next Dose for temozolomide		
\leq Grade 1	No change in dose		
Grade 2	Hold until \leq Grade 1. Resume at same dose level.		
Grade 3	Hold [*] until < Grade 2. Resume at one dose level lower, if indicated. ^{**}		
Grade 4	Off protocol therapy		
*Participants requiring a delay of >30 days should go off protocol therapy. **Participants requiring > two dose reductions should go off protocol therapy.			

Dose reductions of temozolomide during the adjuvant period should be made according to the prescribing information, as summarized below. No dose reductions will be made during the chemoradiation phase. If an adverse event related to temozolomide occurs during chemoradiation, dosing will be held and missed doses will not be made up.

Dose Level	Dose (mg/m2/day)	Remarks
-1	100	Reduction for prior toxicity
0	150	Dose during Cycle 1
+1	200	Dose during Cycle 2 in absence of toxicity

Table: Temozolomide Dose Levels for Cycles 3 and 4

AE's attributed to bavituximab will be managed with maximal supportive care but since temozolomide is the more likely culprit for toxicity, a decrease in temozolomide should be tried prior to stopping bavituximab.

If a patient develops a blood clot, low molecular weight heparin can be used. The bavituximab does not need to be held but may be held at the treating physician's discretion.

